5.3. Exposure of Study Treatment

Exposure for study medications will be summarized separately using SAF by treatment group.

The exposure summary will present descriptive statistics for the following:

- Number of tablets taken
- Number of tablets missed
- Treatment duration (days) = date of last dose date of first dose + 1
- Actual dose = sum of actual tablets administered
- Number of subjects with at least one dose adjustment with a breakdown of reasons for dose adjustment

Overall compliance during the treatment period is calculated as:

% of compliance = (# of tablets taken / # of tablets expected during the treatment period) * 100

By visit summary of compliance will be presented.

All study treatment administration data will be presented in data listings.

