# **5.2.** Administration of Study Treatment

Investigational product (study drug) will be supplied as tablets containing 1 mg liafensine or matching placebo. Study drug will be taken orally, once daily. Patients will be instructed to take the study drug whole, and not to chew, divide, or crush the tablets and take the study drug at the same approximate time each day in the morning.

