2. STUDY DESIGN

2.1. Design Overview

This study will be conducted as a multicenter, randomized, double-blind, placebo-controlled Phase 2b trial to assess the efficacy, safety, tolerability, and PK of liafensine. The study includes an up to 21-day screening period (the screening period may exceed 21 days if a prolonged washout is required).

Approximately 180 patients with TRD who meet all eligibility criteria will be randomized in a 1:1:1 ratio to receive either placebo QD, liafensine 1 mg QD, or liafensine 2 mg QD for 6 weeks. Approximately 150 randomized patients will be genotype GG for DGM4 (DGM4-positive) and approximately 30 randomized patients will be genotype AA or AG for DGM4 (DGM4-negative). DGM4 status (positive vs negative) of randomized patients will be blinded to the sites, patients, and sponsor. An interactive response technology (IRT) system will be used for blinding to DGM4 status, and to achieve the correct randomization ratio of DGM4-positive:DGM4-negative patients by randomly excluding most screened DGM4-negative patients (~80%). Randomization will be stratified by DGM4 status (positive vs negative) and region (North America vs Other). Patients who complete the study or discontinue after randomization will have 2 post-study follow-up visits (14 days after the last administered dose of study drug, and 28 days after the last administered dose of study drug); the 2nd follow-up visit will be conducted via phone call.

The overall study design is shown in Figure 1.

Figure 1. Study Design

Abbreviations: ATRQ = Antidepressant Treatment Response Questionnaire; DGM4 = Denovo Genomic Marker 4; HAMD-17 = Hamilton Depression Rating Scale - 17 Item; QD = once daily; R = randomization.

Patients will be randomly assigned through an IRT system in a 1:1:1 ratio to receive either placebo QD, liafensine 1 mg QD, or liafensine 2 mg QD for 6 weeks.

Randomization Phase:

Placebo QD

• Day 1 through Day 42: two placebo tablets QD

Liafensine 1 mg QD

• Day 1 through Day 42: one 1 mg liafensine tablet and one matching placebo tablet QD

Liafensine 2 mg QD

- Day 1 through Day 7: one 1 mg liafensine tablet and one matching placebo tablet QD
- Day 8 through Day 42: two 1 mg liafensine tablets QD

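### SAP 5.3 defines actual dose as a tablet count, which duplicates another exposure item and does not reflect the liafensine dose assigned to each arm

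*SAP*

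**What the plan says.** SAP 5.3 opens with "Exposure for study medications will be summarized separately using SAF by treatment group" and then lists the items to be described. Among them are "Number of tablets taken", the number missed, treatment duration in days, and "Actual dose = sum of actual tablets administered". Compliance is then defined as tablets taken over tablets expected, as a percentage. None of these lines separates active from placebo tablets, and none gives dose in mg.

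The regimen in SAP 2.1, repeated in protocol 5.1, is:

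- Placebo arm: "Day 1 through Day 42: two placebo tablets QD".
- 1 mg arm: "Day 1 through Day 42: one 1 mg liafensine tablet and one matching placebo tablet QD".
- 2 mg arm, first week: "Day 1 through Day 7: one 1 mg liafensine tablet and one matching placebo tablet QD".
- 2 mg arm, afterwards: "Day 8 through Day 42: two 1 mg liafensine tablets QD".

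Protocol 5.2 gives the tablet strength: "Investigational product (study drug) will be supplied as tablets containing 1 mg liafensine or matching placebo".

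No other section of either document defines dose in mg for the exposure summary.

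**The concern.** The blind is kept by giving every patient the same number of tablets. A rule that adds up tablets therefore measures how long and how regularly a patient took tablets, not how much drug was received. A row labelled actual dose should report drug received.

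What is at stake is modest. One safety objective is to evaluate 1 mg and 2 mg against placebo, and potential liver injury is the adverse event of special interest. A reader of those tables would look to the exposure table for the amount of liafensine behind each column. Under the rule as written, the placebo column would carry a positive actual dose and the two active columns would not differ because of assigned dose. In the pooled 1 mg and 2 mg column, which SAP 3.1 defines as a treatment group, the row would hide that the two regimens deliver different amounts.

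**Working it through.** The documents state no figure for actual dose, so there is none to reproduce. The check is arithmetic on the regimen.

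**Inputs.** Tablets per day and their content come from SAP 2.1, and 1 mg per active tablet from protocol 5.2. Full adherence and 42 dosing days are assumed first.

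**Formulas.**

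- Actual dose as written = sum over days of (active + placebo tablets taken).
- Liafensine received (mg) = sum over days of active tablets taken x 1 mg.

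**Full adherence, 42 days.**

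- Placebo: 42 x 2 = 84 tablets; 42 x 0 = 0 mg.
- 1 mg arm: 42 x 2 = 84 tablets; 42 x 1 = 42 mg, a mean of 1.00 mg/day.
- 2 mg arm: 42 x 2 = 84 tablets; 7 x 1 + 35 x 2 = 77 mg, a mean of 77/42 = 1.83 mg/day.

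**Common earlier stopping days.** The count is again equal across arms.

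| Last dosing day | Tablets, every arm | Placebo, mg | 1 mg arm, mg | 2 mg arm, mg |
|---|---|---|---|---|
| 14 | 28 | 0 | 14 | 7 x 1 + 7 x 2 = 21 |
| 28 | 56 | 0 | 28 | 7 x 1 + 21 x 2 = 49 |
| 42 | 84 | 0 | 42 | 77 |

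**What a missed bottle shows and what it hides.** Protocol Appendix 3 asks patients about one pill from each of two bottles. Assume that active and placebo tablets are in different bottles whenever both are given; the documents do not say so. Take a patient who uses only one bottle for 42 days:

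- Any arm: 42 tablets taken, 42 missed, compliance 42/84 = 50%. The shortfall is visible.
- 1 mg arm: liafensine received is 42 mg or 0 mg, depending on which bottle was used. The count is 42 either way.
- 2 mg arm: Days 8 to 42 give 35 mg whichever bottle was used, because both tablets are active. Days 1 to 7 add 7 mg or 0 mg, for a total of 42 mg or 35 mg.

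So the information lost is whether a missed tablet was active or placebo. It is lost only in the 1 mg arm and on Days 1 to 7 of the 2 mg arm.

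**The case against.** **The authors may have meant active tablets only.** The exposure sentence speaks of medications in the plural, summarized separately, and protocol Table 2 gives a unit dose of 1 mg for liafensine tablets and not applicable for placebo. On that reading the sum equals mg directly: 0, 42 and 77. This may have been the intention, but the text does not say it. The word tablets is unrestricted, and the compliance formula in the same section uses equally unrestricted tablet counts. A programmer following the rule would produce the tablet total.

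**The columns are labelled by arm.** A reader can approximate cumulative mg from the arm label and treatment duration, and nobody would conclude that placebo patients received drug. No analysis in the SAP uses actual dose: safety tables are by treatment group, the per-protocol set uses compliance, administration data are listed in full, and plasma concentrations are collected. All of this stands, and it is why the point is small. The label and duration do not give the mg directly, however, because of the first-week step in the 2 mg arm and because of missed tablets.

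**A reader might infer that under-dosing becomes invisible.** It does not. A missed tablet raises the number missed and lowers compliance, both reported in SAP 5.3.

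**A reader might also infer that the report will show identical doses in all arms.** Equality holds only at equal duration and adherence. Observed counts will differ through missed tablets and early stopping, but not because of assigned dose.

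**Conclusion.** The point holds as a definition error in one descriptive row. Read literally, actual dose repeats the tablet count and takes the value 84 in every arm at full adherence, against 0, 42 and 77 mg of liafensine. Those figures assume 42 dosing days, no missed tablets and the regimen in SAP 2.1. That placebo tablets are counted follows from the unrestricted wording together with the two-tablet regimen; SAP 5.3 does not say it expressly.

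The documents do not support extending this to the trial's conclusions. The primary and secondary efficacy analyses, the alpha level, the sample size and the safety comparisons do not use this variable. Nor do the documents establish that per-bottle counts are in the database. Protocol 5.4 describes counting tablets from returned bottles, and Appendix 3 mentions two bottles, but neither says that counts are stored per bottle or which bottle holds active drug.

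**What to change.** Replace the line in SAP 5.3 with: actual dose (mg) = number of liafensine tablets taken x 1 mg, summed by dosing period using the unblinded kit or bottle assignment. The periods are Days 1 to 7 and Days 8 to 42 in the 2 mg arm, and Days 1 to 42 in the other arms. Keep the tablet count for compliance only. Average daily dose (actual dose divided by treatment duration) is an optional addition.

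First confirm that tablet counts are held per bottle. If they are not, state the allocation assumption in the SAP, for example that missed tablets are split in proportion to the active and placebo tablets dispensed in that period.

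The cost is one line in the SAP and a small programming change. If per-bottle counts exist, no new data are needed; if they do not, one further sentence gives the assumption.

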5.4. Efficacy Analysis

All analyses will be presented for DGM4-positive, DGM4-negative, and both DGM4-positive and DGM4-negative subjects.

The analyses of the primary and key secondary efficacy endpoints will be conducted on the FAS. Supportive sensitivity analyses will be performed in the per protocol analysis set for primary and key secondary efficacy endpoints unless otherwise specified.

5.4.1. Primary Endpoint: Change in MADRS Total Score from Baseline to Day 42, in DGM4-Positive Patients

5.4.1.1. Estimand

The following components are considered in the construction of the estimand, the main clinical quantity of interest to be estimated in the study:

- Objective: To demonstrate that liafensine (1 mg QD or 2 mg QD) is superior to placebo in DGM4-positive patients with TRD as assessed by the change in MADRS total score from baseline to Day 42 of double-blind treatment
- Intercurrent events (ICEs): Early termination of treatment due to various reasons or starting a prohibited medication. A detailed list of ICEs is provided at the end of this section.
- Question of interest: For a patient with TRD for whom a short-term monotherapy would be indicated, what would be the expected effect of liafensine on severity of depressive

episodes at Week 6, if taken as directed for 6 weeks without initiating prohibited medications as defined in Protocol Section 5.3?

The primary estimand is defined with the following components per ICH E9(R1):

- The treatment condition of interest: TRD patients who meet all eligibility criteria will be randomized in a 1:1:1 ratio to receive either placebo QD, liafensine 1 mg QD, or liafensine 2 mg QD for 6 weeks.
- Population: patients with TRD with the DGM4-positive biomarker
- Endpoint at subject level: change in MADRS total score from baseline (Visit 3, Day -1) to Day 42 (Visit 7)
- Population-level summary: For each treatment arm, the least-square (LS) mean of the primary endpoint will be calculated in each arm using the method described in Section 5.4.1.2. Treatment comparisons will be based on the LS means.

Intercurrent events and corresponding strategies:

Intercurrent events to be considered for this analysis are those events that cause the MADRS at Day 42 to be either missing or compromised. The primary method will be mixed model for repeated measures (MMRM) with imputation assuming missing at random (MAR), ie, a hypothetical strategy per ICH E9(R1). Hence, missing values will be imputed with non-missing values in the same treatment group. A fully conditional specification (FCS) method with predictive mean matching approach will be used in the imputation of missing MADRS score change from baseline as continuous variables (Buuren 2007). The following sensitivity analyses will be performed, with details described in Section 5.4.1.3:

- A tipping-point analysis for the primary analysis result
- MMRM without imputation
- MMRM with multiple imputation using a patter-mixture model, as well as a tipping point analysis for this imputation method
- Sensitivity analyses based on RAS

MMRM will be implemented using SAS Mixed procedure with the default REML (restricted maximum likelihood) estimation.

ICEs in this study are listed below:

- Treatment discontinuation due to AE
- Withdrawal of consent to treatment discontinuation
- Other/Lost to follow-up
- Use of prohibited medications
- Pregnancy
- Death

5.4.1.2. Main Estimator

The primary efficacy analysis will be performed in DGM4-positive patients at 1-sided significance level of 0.05 using MMRM with imputation based on the MAR assumption. The model will include the fixed effects of treatment, visit (categorical covariate), treatment-by visit interaction, treatment by baseline MADRS total score, baseline MADRS total score (continuous covariate), and region. Change from baseline in weekly visits at Days 7, 14, 28, and 42 will be

the repeated outcome measures, and the model will use an unstructured variance-covariance matrix. If the model does not converge the algorithm (Lu 2010) will be used to assist in the convergence.

The following hypothesis will be tested based on the test statistics from the mixed model:

 $H_0: u_i - u_0 = 0 \text{ vs. } H_A: u_i - u_0 \neq 0$

where u_i is the expected mean change from baseline in MADRS for liafensine at Day 42 and u_0 is the expected mean change from baseline in MADRS for placebo at Day 42. In H₀ and H_A above, i = 1, 2, 3 are for liafensine 1 mg, 2 mg, and both arms pooled, respectively, for implementing the closed testing procedure described in Section 3.7. The LSMESTIMATE statement in SAS Mixed procedure will be used to test the global null hypothesis of no treatment difference between both active arms and placebo while keeping all 3 treatment groups separately. Please see sample SAS code in Appendix 8.2.

The LS mean for change from baseline in MADRS total score at Day 42 for the combined liafensine treatment arms (1 mg QD and 2 mg QD) and placebo arm will be estimated from the MMRM model. The comparison of the change in MADRS total score from baseline to Day 42 between each of the two liafensine treatment arms and placebo will be carried out using the same approach. Separate figures with the mean change (\pm SD) and LS mean change (\pm SE) by visit will be displayed.

In the analysis, data collected after initiation of prohibited medications will be used unless otherwise specified. All available data collected from all subjects before or after ICEs will be included in the analysis unless otherwise specified. Missing data due to any ICEs will be imputed using SAS MI procedure with the FCS statement and REGPMM option to implement the fully conditional specification method with predictive mean matching approach described in Section 5.4.1.1. For MADRS, the total score is set to missing if 50% or more items are missing at an assessment. When this occurs, the change from baseline value will be imputed without using any of the non-missing items.

The following variables will be included in the imputation model: region, baseline MADRS score, and change from baseline at Weeks 1, 2, 4, and 6. One hundred fully imputed datasets will be created. The MMRM described above will be used for treatment comparisons. Treatment effects (difference in LS means between treatment arms) from these 100 analyses will be combined to generate final results using Rubin's method implemented by SAS MIANALYZE procedure.

The following tables and figures will be generated to assess the MAR assumption:

- 1. A by-visit and overall summary table for (n, %), and cumulative (n, %) for reasons of missing value or early dropout in each arm due to:
 - AE including death
 - Withdrawal of consent to treatment discontinuation
 - Other reasons
 - Total (All of the above)

Within each arm, the summary statistics of the primary endpoint will also be generated by dropout reason at each visit. This table will also be used to support the figure below.

- 2. For each arm, generate a line graph for mean change from baseline (y-axis) over time (x-axis) by dropout reasons. There will be 4 lines on this figure to represent each dropout reasons:
 - None (completers)
 - Dropout due to AE including death
 - Dropout due to withdrawal of consent to treatment discontinuation
 - Dropout due to other reasons

In addition, a figure similar to the one above will be generated, with mean change from baseline replaced with a line graph for each subject. Subjects with the same reason for dropout will have the same color.

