## 8.3.3. Efficacy Analyses

The primary efficacy endpoint is the change in MADRS total score from baseline (Visit 3, Day -1) to Day 42 (Visit 7). The primary efficacy analysis will be performed in DGM4-positive patients at 2-sided significance level of 0.05 using a mixed model for repeated measures (MMRM) that includes the fixed effects of treatment, visit (categorical covariate), treatment-by-visit interaction, baseline MADRS total score (continuous covariate), and region. An unstructured variance-covariance matrix will be used. The least-squares (LS) mean change in MADRS total score at Day 42 from baseline for the combined liafensine treatment arms (1 mg QD and 2 mg QD) and placebo arm will be estimated from the MMRM model. The treatment effect for the combined liafensine treatment arms vs placebo will be estimated using the LS mean difference at Day 42 from the MMRM model. The comparison of the change in MADRS total score from baseline to Day 42 between each of the 2 liafensine treatment arms and placebo will be carried out using the same approach. The key secondary efficacy endpoint for this study is the change in CGI-S from baseline (Visit 3, Day -1) to Day 42 (Visit 7), in DGM4-positive patients.

Other secondary and exploratory efficacy endpoints include the CGI-I, SDS, response (defined as  $\geq$  50% improvement from baseline in MADRS total score at Day 42), and remission (defined as MADRS total score  $\leq$  10 at Day 42), in DGM4-positive patients. CGI-S, CGI-I, and SDS will be analyzed using the same MMRM model as for the primary efficacy endpoint. Response rate, remission rate, and corresponding 95% confidence interval (CI) for each treatment group will be derived by using Clopper-Pearson method. The comparison of response rate and remission rate between treatment groups will be carried out using the Cochran–Mantel–Haenszel (CMH) test.

Subscales, individual items, and domains of endpoints will also be analyzed in an exploratory manner, using the same MMRM model as for the primary efficacy endpoint.

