The same model in the primary analysis will be used without imputation using the treatment policy strategy per ICH E9(R1) (Polverejan 2023). This analysis will be used to assess the impact of imputing missing values based on the MAR assumption.

3. MMRM with imputation using pattern mixture model

This sensitivity estimator will be using a control-based multiple imputation method (Ratitch 2013). This sensitivity analysis does not rely on the MAR assumption. Data collected after initiation of prohibited medications will not be used unless otherwise specified. Missing data due to all ICEs will be handled per specifications below unless otherwise specified.

In this sensitivity analysis, imputation will be implemented using SAS MI procedure with FCS statement and REGPMM option, as well as MNAR statement with MODELOBS option to identify observations from the placebo arm for deriving the imputation models, ie, assuming all missing data will have a profile that equals the profile of the placebo arm for all time points. The variables to be used in the imputation are region, baseline values, and change from baseline values observed at Weeks 1, 2, 4, and 6.

One hundred fully imputed datasets will be created. The MMRM described in Section 5.4.1.2 will be used for treatment comparisons. Treatment effects (difference in LS means between treatment arms) from these 100 analyses will be combined to generate the final results using Rubin's method with SAS MIANALYZE procedure.

A tipping point analysis for this sensitivity analysis will also be conducted to assess the robustness of the result. The same steps described in the first sensitivity analysis will be followed.

4. Sensitivity Analyses based on RAS

A set of sensitivity analyses listed below will be performed using DGM4-positive patients in RAS. The same MMRM in the primary and sensitivity analyses described above will be carried out with the exclusion of the following fixed effect: treatment by baseline MADRS total score. In other words, the model will include the fixed effects of treatment, visit (categorical covariate), treatment by visit interaction, baseline MADRS total score (continuous covariate), and region.

The following analyses will be performed in this set of sensitivity analyses:

- 1) The primary analysis, as well as the 1st and 2nd sensitivity analyses based on FAS will be repeated using RAS.

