6. CHANGES FROM ANALYSES PLANNED IN THE PROTOCOL

Changes from the protocol-specified analyses are listed in Table 4.

Protocol	SAP	Justification
Section 8.3.3.1: The family- wise type I error rate will be controlled at a fixed 1-sided alpha level of 0.025 using a closed testing procedure for multiple dose comparisons and multiple endpoint comparisons in DGM4-positive patients.	Section 3.7: All statistical tests for the treatment comparison of efficacy endpoints will be based on a 1-sided alpha level of 0.05.	In this Phase 2b study, the sample size was not powered for testing superiority with multiplicity adjustment for each dose.
Section 8.3.3: The primary efficacy analysis will be performed in DGM4-positive patients at 2-sided significance level of 0.05 using a mixed model for repeated measures (MMRM) that includes the fixed effects of treatment, visit (categorical covariate), treatment-by-visit interaction, baseline MADRS total score (continuous covariate), and region.	Section 5.4.1.2: The primary method will be mixed model for repeated measures (MMRM) with imputation assuming missing at random (MAR), ie, a hypothetical strategy per ICH E9(R1). Hence, missing values will be imputed with non- missing values in the same treatment group. A fully conditional specification and predictive mean matching method will be used in the imputation. The following variables will be included in the imputation model: region, baseline MADRS score, and change from baseline at Weeks 1, 2, 4, and 6. One hundred fully imputed datasets will be created. The MMRM described in Section 5.4.1.2 will be used for treatment comparisons. Treatment effects (difference in LS means between treatment arms) from these 100 analyses will be combined to generate the final results using Rubin's method with SAS MIANALYZE procedure.	 With multiple imputation, all subjects in the full analysis set will have a value at the primary time point, ie, Day 42, for treatment comparisons. Since the original method in the protocol assumes missing at random, the same assumption will be used in multiple imputation. This method allows for performing a tipping point analysis to assess the robustness of the results under the MAR assumption.

7. **REFERENCES**

Buuren SV. Multiple imputation of discrete and continuous data by fully conditional specification. Stat Methods Med Res. 2007;16(3):219–242.

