8. APPENDIX: SAMPLE SAS CODES

The sample SAS codes provided in this section are for reference only. The actual SAS codes to generate the tables will be checked through QC process. For sensitivity analyses using RAS, use the dataset flag for RAS and exclude GPN*base, ie, treatment-by-baseline-score interaction, in the model statement in Proc Mixed.

8.1. SAS Code for Multiple Imputations Based on the Non-missing Values in the Same Arm with FCS and REGPMM Options

```
%let nimpute=100;
%let seed=10401;
proc sort data=adqs4 out=adqs5;
where avisitn in (40 50 60 70) and dgmn=1 and gpn^{3};
by trt01pn usubjid dgmn gpn region base avisitn;
run:
proc transpose data=adqs5 out=cfb;
 by GPN usubjid dgmn region base;
 var chg;
 id avisitn;
run;
*** Imputation using fully conditional specification and predictive mean matching methods;
proc mi data=cfb(rename=( 40=cfb1 50=cfb2 60=cfb4 70=cfb6)) nimpute=&nimpute
seed=&seed out=fcs;
 by GPN;
 class region;
 var region base cfb1 cfb2 cfb4 cfb6;
 FCS REGPMM;
run:
```

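### No MMRM in the protocol or SAP lets the baseline MADRS slope differ by visit; adding baseline-by-visit is a small, low-cost improvement at Day 42

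*SAP*

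**What the plan says.** Both documents plan a repeated-measures model for change in MADRS, with an unstructured covariance matrix.

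- **Protocol 8.3.3** lists "fixed effects of treatment, visit (categorical covariate), treatment-by-visit interaction, baseline MADRS total score (continuous covariate), and region".
- **SAP 5.4.1.2** lists treatment and visit, then "treatment-by visit interaction, treatment by baseline MADRS total score, baseline MADRS total score (continuous covariate), and region". The MODEL statement in SAP 8.2 agrees: it contains GPN*base and no base*AVISITN.
- **Other FAS analyses (SAP 5.4.1.3).** For item 2, "The same model in the primary analysis will be used without imputation". Item 3 also refers back to the 5.4.1.2 model.
- **RAS analyses (SAP 5.4.1.3, item 4).** "The primary analysis, as well as the 1st and 2nd sensitivity analyses based on FAS will be repeated using RAS", but "with the exclusion of the following fixed effect: treatment by baseline MADRS total score". The introduction to SAP Section 8 says the same: "exclude GPN*base, ie, treatment-by-baseline-score interaction, in the model statement in Proc Mixed".
- **SAP Table 4** sets the protocol's fixed effects against the SAP method. Its SAP column says "The MMRM described in Section 5.4.1.2 will be used for treatment comparisons". The justification concerns imputation, beginning "With multiple imputation, all subjects in the full analysis set will have a value at the primary time point". It does not mention treatment-by-baseline.

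No analysis model in either document contains baseline-by-visit.

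**The concern.** Treatment-by-visit is in the model, so each arm has its own mean at each visit. The baseline adjustment has no such freedom. The protocol model uses one slope for all four visits. The SAP model uses one slope per arm, again the same at all four visits.

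In a depression trial the relation between baseline score and change may well strengthen from Day 7 to Day 42. A common slope is a weighted compromise across visits. The early visits have the smallest residual variance and therefore dominate it. The Day 42 contrast, the only one used for the primary test, is then corrected for chance baseline imbalance with a slope that is too shallow. Precision is lost at exactly that visit.

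At stake is a little efficiency. Validity is not in question.

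**Working it through.** **1. The plan's own figure.** Inputs from Protocol 8.2 and SAP 2.3: difference 4.5, SD 9, 2-sided alpha 0.05, power 80%, two active arms pooled against placebo (2:1).

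n = (1.960 + 0.842)² × 9² × (1 + 1/2) / 4.5² = 47.09 per arm.

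Power with 94 vs 47 is 79.9%. Allowing 5%: 47/0.95 = 49.5, so 50 per arm. The stated 47 and 50 reproduce.

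**2. Assumed inputs.** The documents give no slopes, baseline SD, visit correlations or dropout rate. I assumed:

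- residual SDs 5, 6.5, 8, 8.5 at Days 7, 14, 28, 42;
- correlations 0.7 (D7-D14), 0.6 (D7-D28), 0.5 (D7-D42), 0.7 (D14-D28), 0.6 (D14-D42), 0.8 (D28-D42);
- baseline SD (sb) of 4, 5 or 6;
- slopes b by visit: constant (-0.3 throughout); moderate (-0.1, -0.2, -0.3, -0.4); steep (-0.05, -0.15, -0.35, -0.5).

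**3. The common slope.** With one slope, generalized least squares gives c = (1'W⁻¹b)/(1'W⁻¹1), where W = Σ + sb²(b−c)(b−c)', iterated. The resulting weights on the four visits are 0.893, 0.102, −0.098 and 0.103.

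- Moderate: 0.893(−0.1) + 0.102(−0.2) − 0.098(−0.3) + 0.103(−0.4) = −0.12, against −0.4 at Day 42.
- Steep: 0.893(−0.05) + 0.102(−0.15) − 0.098(−0.35) + 0.103(−0.5) = −0.08, against −0.5 at Day 42.

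**4. Gross loss at Day 42.** The unadjusted part of the slope adds sb²(b₄₂ − c)² to the residual variance 8.5² = 72.25. For the moderate slopes at sb = 5: 1 + 25 × 0.278²/72.25 = 1.027.

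| Slopes | Variance ratio, sb = 4 / 5 / 6 | SE increase |
|---|---|---|
| Constant | 1.000 / 1.000 / 1.000 | 0% |
| Moderate | 1.017 / 1.027 / 1.039 | 0.9-1.9% |
| Steep | 1.040 / 1.062 / 1.089 | 2.0-4.4% |

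**5. Net of degrees of freedom.** Simulated REML MMRM without imputation, 47 per arm, sb = 5, 1,000 runs per scenario. Mean Day 42 SE, pooled doses vs placebo:

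| Slopes | Day 42 dropout | SAP model | SAP model + baseline-by-visit | Effect of adding the term |
|---|---|---|---|---|
| Constant | 0 | 1.522 | 1.526 | costs 0.3% |
| Moderate | 0 | 1.541 | 1.525 | gains 1.0% |
| Steep | 0 | 1.567 | 1.526 | gains 2.7% |
| Constant | 20% | 1.606 | 1.611 | costs 0.3% |
| Moderate | 20% | 1.637 | 1.621 | gains 1.0% |
| Steep | 20% | 1.662 | 1.618 | gains 2.7% |

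A complete-data simulation under other assumptions (50 per arm, residual SD rising from 5 to 9, slopes −0.1 to −0.5) gave 1.556 to 1.560 with constant slopes and 1.583 to 1.560 with varying slopes. The mean estimate stayed near −4.5 under every model.

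**6. Effect on sizing.** SD of change at Day 42 is √(8.5² + (b₄₂ × sb)²), or 8.58 to 9.01 over all cases. Power at 9.01 is 79.8%, against 79.9% at 9.

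**7. The treatment-by-baseline term.** In the runs of step 5, and in matching runs with a true interaction of −0.2, dropping it moved the Day 42 estimate by an SD of 0.08 to 0.10 point. The mean shift was under 0.01 point. The 1-sided 0.05 verdict changed in 0.3-1.5% of runs.

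A patient with no post-baseline MADRS contributes no outcome row to an MMRM without imputation. The planned no-imputation RAS run is therefore practically the protocol's model in the FAS. In simulation, assuming the added RAS patients had no post-baseline MADRS, the two fits were identical. The model effect seen in the planned no-imputation FAS-RAS pair tracked the model effect under imputation with correlation 0.97-1.00.

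**The case against.** **Baseline-by-visit is a modelling preference.** Neither document has the term, so nothing is contradicted. The gain depends on slopes the documents do not give, and with constant slopes the SE gets slightly worse. This stands, and it is why the point is minor. The balance still favours the term: a net cost of about 0.3% against a net gain of 1.0-2.7% at baseline SD 5. The 4.4% in step 4 is gross and belongs to the steepest slopes with the largest baseline SD, so it should not be set against the 0.3%.

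**The imputation already allows visit-specific slopes.** Within each arm, baseline is a predictor at every visit (SAP 8.1). That is true for the imputed values only. The MMRM fitted afterwards still forces a common slope on all the data.

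**The SAP is at Version 2 and has been submitted.** Reopening a primary model for a 1-3% gain that may not appear is not free. This also stands, so the fix offers a fallback.

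**Stronger readings.** A reader might infer that the SAP concealed a change of primary model. It did not: Table 4 points to Section 5.4.1.2, where treatment-by-baseline is written out, and 5.4.1.3 and Section 8 name it as well. A reader might also infer that no planned analysis separates the effect of that term from the change of population. The imputed FAS-RAS comparison does change both, but the no-imputation pair already shows the model effect in practice.

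**Conclusion.** A minor, low-cost improvement. The absence of baseline-by-visit from every model is a fact of the text. Its price is conditional. If baseline slopes grow across visits as assumed, the Day 42 SE is about 1-3% larger than necessary, net of degrees of freedom. If slopes are constant, nothing is lost and adding the term would cost about 0.3%. All slopes, SDs and correlations are my assumptions.

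The documents do not support reading this as bias or as a threat to the primary result. Randomization makes baseline independent of arm, so a slope that is too shallow leaves chance imbalance partly uncorrected but does not shift the estimate on average. The sample size is unaffected.

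The silence of Table 4 on treatment-by-baseline, and the loose reference to a similar model for CGI-S in SAP 5.4.2, are documentation matters with almost no numerical consequence.

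**What to change.** Before unblinding:

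1. Add base*AVISITN to the MODEL statement in SAP 8.2 and to the fixed effects in SAP 5.4.1.2 and 5.4.1.3 item 4, for FAS and RAS alike, and record it in Table 4. The cost is 3 fixed-effect degrees of freedom (about 0.3% in SE if slopes are constant) and an amendment to a submitted SAP. No change to sample size is needed.
2. If the sponsor will not amend the primary model, prespecify the same model as an FAS sensitivity analysis. It can use the datasets already imputed.
3. In the same amendment, as housekeeping: name and justify treatment-by-baseline in Table 4, or drop it so that FAS and RAS share the same fixed effects; and state in 5.4.2 which terms apply to CGI-S. This is a few lines of text.
4. Optional: one FAS run with the protocol's fixed effects. It would carry a clearer label but add little to the planned no-imputation RAS run.
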